12.1.2. Determining Severity of Adverse Events

AEs must be graded for severity (ie, intensity) using CTCAE, version 5.0 ([HHS 2017](#)). A severity category of mild, moderate, severe, life-threatening, or death, as defined in [Appendix B](#), must be entered on the AE eCRF. The criteria below are to be used for determining the severity of AEs where there is no actual CTCAE term for the specific reported AE found in the CTCAE, version 5.0 guideline ([Appendix B](#)). It should be noted that the term “severe” used to grade intensity is not synonymous with the term “serious”. The assessment of severity is made regardless of the relationship to study drug or of the seriousness of the AE. When reporting AEs, reference should be made to the CTCAE manual for guidance on appropriate grading.

- Grade 1: Mild; asymptomatic or mild symptoms; clinical or diagnostic observations only; intervention not indicated.
- Grade 2: Moderate; minimal, local or noninvasive intervention indicated; limiting age-appropriate instrumental activities of daily living (eg, preparing meals, shopping for groceries or clothes, using the telephone, managing money).
- Grade 3: Severe or medically significant, but not immediately life-threatening; hospitalization or prolongation of hospitalization indicated; disabling, limiting selfcare activities of daily life (eg, bathing, dressing and undressing, feeding self, using the toilet, taking medications, not bedridden).
- Grade 4: Life-threatening consequences; urgent intervention indicated.
- Grade 5: Death related to AE.

12.1.3. Determining Causality of Adverse Events

Causality refers to the relationship of the event to the study drug (EP262 or placebo). The Investigator will assess the causality of the event according to the following criteria:

- **Not related** – A reaction for which sufficient data exist to indicate that the etiology is unrelated to the study drug.
- **Related** – A reaction that follows a reasonable temporal sequence from administration of study drug; that follows a known or expected response pattern to the study drug, which may or may not reasonably have been produced by a number of other factors including underlying disease, complications, concomitant drugs, or concurrent treatments; and/or that could not be reasonably explained by other factors such as underlying disease, complications, concomitant drugs, or concurrent treatments; and/or disappears or decreases on cessation or reduction in study drug dose; and/or reappears or worsens when the study drug is administered.

12.1.4. Recording Adverse Events

All AEs must be recorded in the source documents and in the eCRFs provided by the Sponsor from the signing of the Informed Consent Form (ICF) until the end of study participation. AEs will be assessed for likelihood of causal relationship to the study drug (EP262 or placebo) and severity.

The new onset of signs, symptoms, or other findings that occur before signing of the ICF will be captured as medical history (Section [12.3](#)).

12.1.4.1. Special Instructions for Recording Adverse Events in the eCRF

Diagnosis versus Signs and Symptoms

If a diagnosis is known at the time of reporting, this should be recorded in the eCRF rather than the individual signs and symptoms (eg, record only hepatitis rather than elevated transaminases, bilirubin, and jaundice). However, if a constellation of signs and/or symptoms cannot be medically characterized as a single diagnosis or syndrome at the time of reporting, each individual event should be recorded as an SAE or AE on the eCRF. If a diagnosis is subsequently established, it should be reported as follow-up and should replace the individual signs and/or symptoms as the event term on the eCRF, unless the signs/symptoms are clinically significant.

Adverse Events Occurring Secondary to Other Events

In general, AEs occurring secondary to other events (eg, clinical sequelae or a cascade of events) should be identified by their primary cause. For example, if severe vomiting is known to result in dehydration, it is sufficient to record only vomiting as an SAE or AE on the eCRF. However, medically significant AEs occurring secondary to an initiating event that are separated in time should be recorded as independent events on the eCRF. For example, if severe vomiting leads to acute renal failure, both events should be recorded on the eCRF.

Persistent or Recurrent Adverse Events

A persistent AE is one that extends continuously, without resolution, between subject evaluation timepoints. Such events should only be recorded once on the eCRF. If a persistent AE becomes more severe or lessens in severity, it should be recorded as a new AE on the eCRF.

A recurrent AE is one that occurs and resolves between subject evaluation timepoints, and subsequently recurs. Each reoccurrence of an AE should be recorded on the eCRF.

Abnormal Laboratory Values or Vital Signs

Protocol defined laboratory values and vital signs will be reported as AEs if the abnormal laboratory or vital sign result:

- Requires an adjustment in the study drug(s) or discontinuation of treatment;
- Requires additional testing, excluding repeat testing of the lab in question, or surgical intervention;
- Is associated with accompanying signs/symptoms that are not considered part of a preexisting diagnosis or syndrome; or
- Is considered clinically significant by the Investigator

If an abnormal laboratory value or vital sign is the result of an evaluation of clinical signs, symptoms, or suspected diagnosis during the conduct of the study, the signs/symptoms or diagnosis should be reported as an AE (or if appropriate, an SAE) only if clinically significant, and the associated laboratory value or vital sign should be considered additional information that must be collected on the relevant eCRF.

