12.1. Adverse Events

12.1.1. Definition of an Adverse Event

An AE is defined as any untoward medical occurrence in a subject administered a pharmaceutical product and which does not necessarily have a causal relationship with this treatment. An AE can therefore be any unfavorable or unintended sign (including a clinically significant abnormal laboratory finding), symptom, or disease temporally associated with the use of a medicinal (investigational) product.

Medical conditions present at baseline that worsen in severity or frequency after exposure to study drug are considered TEAEs. A TEAE is any condition that was not present prior to treatment with the study drug but appeared following treatment, was present at treatment initiation but worsened during treatment, or was present at treatment initiation but resolved and then reappeared while the individual was on treatment (regardless of the intensity of the AE when the treatment was initiated). Planned hospital admissions or surgical procedures for an illness or a disease that existed before administration of study drug, and for which the condition has not worsened since starting study drug, are not to be considered TEAEs/treatment-emergent SAEs. Events with emergency room visits that are less than 24 hours will also not be considered SAEs unless they meet one of the criteria listed in Section [12.2.1](#).

Clinically significant abnormal laboratory tests, 12-lead ECG assessments, or vital sign results may constitute an AE if they meet one of the criteria listed in Section 12.1.4.1. However, whenever possible, the underlying diagnosis should be listed in lieu of associated abnormal results. Abnormalities deemed not clinically significant by the Investigator should not be reported as AEs.

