16.9. Safety Analysis

The Safety Analysis Set will be used for the summaries of the safety data. Safety data will be summarized by treatment group and overall.

The safety and tolerability of EP262 will be assessed by comparing the frequency, causality, and severity of AEs as well as treatment discontinuations due to AEs. AEs will be coded using the Medical Dictionary for Regulatory Activities (MedDRA) by System Organ Class and preferred term. AEs that begin after the first administration of study drug, or existing AEs that worsen after the first dose of study drug, are considered treatment emergent. All AE summaries will include TEAEs, and all AEs will be presented in data listings.

Concomitant medications will be coded using the World Health Organization (WHO) Drug Dictionary and summarized descriptively by Anatomic Therapeutic Chemistry (ATC) class using counts and percentages. Medications started prior to the first dose of study drug will be indicated in the data listings. Use of rescue medications will also be summarized.

Changes in vital signs, standard 12-lead ECGs, and laboratory evaluations will be summarized descriptively.

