#### **4.5.3 Adverse Events**

Treatment-emergent adverse events (TEAEs) are defined as those AEs with onset after the first dose of study drug or existing events that worsened after the first dose during the study. Treatment-emergent AEs will be summarized by treatment group within each study part, pooled treatment groups, and over all subjects combined. Events reported with a partial onset date (e.g., month and year are reported but the day is missing) will be considered to be treatment-emergent if it cannot be confirmed that the event onset was prior to the first dose of study drug based on the available date entries.

Verbatim terms on case report forms will be mapped to preferred terms and system organ classes using MedDRA, version 26.0.

Summaries that are displayed by system organ class and preferred terms will be ordered by descending incidence of system organ class and preferred term within each system organ class. Summaries displayed by preferred term only will be ordered by descending incidence of preferred term. Summaries of the following types will be presented:

- Overall summary of number of unique TEAEs and treatment-emergent serious adverse events (SAEs) and subject incidence of TEAEs meeting various criteria;
- Subject incidence of TEAEs by MedDRA system organ class and preferred term;

- Subject incidence of the most frequently-occurring TEAEs (i.e., TEAEs occurring in  $\geq 10\%$  of the Safety Analysis Set) by MedDRA preferred term;
- Subject incidence of TEAEs by severity grade, MedDRA system organ class, and preferred term;
- Subject incidence of TEAEs by relationship to study drug, MedDRA system organ class, and preferred term;
- Subject incidence of the most frequently-occurring TEAEs related to study drug (i.e., related TEAEs occurring in  $\geq 10\%$  of the Safety Analysis Set) by MedDRA preferred term;
- Subject incidence of severe TEAEs related to study drug by MedDRA system organ class and preferred term; and
- Subject incidence of SAEs by MedDRA system organ class and preferred term.

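### An adverse event that begins before dosing and only improves afterwards can be flagged treatment-emergent under SAP 4.5.3, although SAP 3.4.2.1 says it is not

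*Protocol*

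**What the plan says.** **Recording.** Under Protocol 12.1.4, AEs are recorded "from the signing of the Informed Consent Form (ICF) until the end of study participation". Earlier conditions go elsewhere: "The new onset of signs, symptoms, or other findings that occur before signing of the ICF will be captured as medical history". For a persistent AE, Protocol 12.1.4.1 first says "Such events should only be recorded once on the eCRF", then adds "If a persistent AE becomes more severe or lessens in severity, it should be recorded as a new AE on the eCRF". It does not say what onset date the new record carries.

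**Flagging, by onset.** SAP 4.5.3, which governs the TEAE tables, defines TEAEs as "those AEs with onset after the first dose of study drug or existing events that worsened after the first dose during the study". Protocol 16.9 is equivalent: "AEs that begin after the first administration of study drug, or existing AEs that worsen after the first dose of study drug".

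**Flagging, by condition.** Protocol 12.1.1 begins: "A TEAE is any condition that was not present prior to treatment with the study drug but appeared following treatment". It then adds two further routes: a condition present at the start of treatment that worsened, and one that resolved and came back on treatment. SAP 3.4.2.1 repeats this definition. None of the three routes covers improvement.

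**Counting.** SAP 4.5.3 counts a subject once at each level of summary (any AE, system organ class, preferred term). It also reports the number of unique TEAEs but does not define unique.

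**The concern.** The recording rule splits one continuous event into several records, and the rule that drives the tables classifies by onset after first dose. Neither document says how records of one event are joined before flagging or counting. An AE arising in screening that eases after Day 1 therefore has a second record that can meet the onset test in SAP 4.5.3, although nothing new or worse has happened to the subject.

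TEAE frequency and severity form a secondary endpoint (Protocol Section 6). The SAP introduction says its descriptions are there to prevent post hoc decisions. As written, the programmer would have to choose between two TEAE definitions that give opposite answers for the same record. If the onset rule is followed, some subjects are counted as having a TEAE when by the plan's own condition-based definition they had none.

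**Working it through.** The plan states no AE rate or TEAE count that could be reproduced, so the check is a trace of the rules.

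**Which events are exposed.** Consent is taken at Visit 1, between Day -30 and Day -14, so every subject has at least two weeks before dosing in which an AE record can be opened. Conditions from before consent are medical history and have no AE record to split.

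**Trace, taking the new record's onset as the date of change:**

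| Case | AE records | SAP 4.5.3 / Protocol 16.9 | Protocol 12.1.1 / SAP 3.4.2.1 |
|---|---|---|---|
| A. Starts in screening at Grade 2, eases to Grade 1 on Day 5 | 2 | TEAE (second record) | Not a TEAE |
| B. Starts in screening at Grade 1, worsens to Grade 2 after dosing | 2 | TEAE | TEAE |
| C. Starts in screening, resolves, reappears on treatment | 2 | TEAE | TEAE |
| D. Starts after dosing at Grade 3, eases through Grades 2 and 1 | 3 | TEAE | TEAE |
| E. Present before consent, improves after dosing | 0 | Not a TEAE | Not a TEAE |

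Only case A gives conflicting flags. In case D the flag is right under both definitions and subject incidence does not change, because the subject is counted once. Only the number of unique TEAEs is open: one or three, depending on what unique means.

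**Effect of one case A subject.** If the subject has no other TEAE at that level of the table, incidence rises by 100/n percentage points. With the planned group sizes in SAP 4.6:

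- 25 mg, n = 30: 100/30 = 3.3 points
- 50 mg and 150 mg, n = 38 each: 100/38 = 2.6 points
- pooled placebo, n = 48: 100/48 = 2.1 points

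**Illustration with assumed inputs (not in the documents).** Let p be the true proportion of subjects with any TEAE and q the proportion with a case A event, taken as independent. Observed incidence is p + (1 − p)q, so the excess is (1 − p)q.

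| p | q | Excess |
|---|---|---|
| 0.30 | 0.02 | 0.70 × 0.02 = 1.4 points |
| 0.30 | 0.10 | 0.70 × 0.10 = 7.0 points |
| 0.50 | 0.02 | 0.50 × 0.02 = 1.0 point |
| 0.50 | 0.10 | 0.50 × 0.10 = 5.0 points |

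Over these inputs the excess runs from 30 × 0.010 = 0.3 subjects to 48 × 0.070 = 3.4 subjects per group. This shows scale only.

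**The case against.** The strongest reply is that the plan already excludes case A. Protocol 12.1.1 and SAP 3.4.2.1 define a TEAE by condition, and a pre-dose condition that only improves meets none of their routes. SAP 4.5.3 can be read the same way. Since worsening also opens a new record, its second limb, on existing events that worsen, would have little to do if every new record were a fresh onset. That limb suggests a continuing event stays an existing event and qualifies only by worsening. The onset date for the new record is also unstated, and the eCRF instructions are not among the documents.

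This stands as evidence of intent, and it rules out calling the misclassification certain. It does not supply a rule that can be programmed. The condition-based definition cannot be applied to separate records until something identifies which records continue which event, and SAP 4.5.3 has no such step. Its default for partial onset dates is to treat an event as treatment-emergent unless pre-dose onset is confirmed.

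Three stronger readings are tempting, but the documents do not support them:

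- A reader might infer that an event resolving from Grade 3 through Grades 2 and 1 inflates the TEAE tables threefold. The tables by organ class, preferred term, severity and relationship report subject incidence and do not move. Only the unique event count might.
- A reader might infer that an effective drug would show more TEAEs because it eases existing complaints. Complaints from before consent, including established urticaria, are medical history and cannot follow this path. The rule is the same in every arm, and nothing in the documents points to different improvement of incidental screening events by arm.
- A reader might see Protocol 12.1.4.1 as contradicting itself. Recording an event once, except when its severity changes, is a general rule with an exception.

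**Conclusion.** The point holds in limited form. For an AE that starts between consent and first dose and afterwards only improves, the rule behind the TEAE tables and the condition-based definition give opposite answers. Followed literally, with onset set to the date of change, Protocol 12.1.4.1 and SAP 4.5.3 count it as a TEAE against SAP 3.4.2.1.

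The effect is one extra subject per such case, and only where that subject has no other TEAE at the same level of the table. The total cannot be derived, because the documents give neither the frequency of such events nor the onset date convention. A bias between arms would need improvement of these events to differ by arm, which the documents do not show. The matter should be settled before lock because it affects a secondary endpoint and the correction is small.

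**What to change.** Amend SAP 4.5.3 as follows, and align Protocol 16.9 or list the difference in SAP 4.7:

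1. State that treatment emergence follows the condition-based definition in SAP 3.4.2.1.
2. Link consecutive AE records of one continuous event: same subject, same preferred term, and a new start date at or next to the previous end date.
3. State that a linked continuation at the same or a lower grade than the pre-dose record is not treatment-emergent. A continuation at a higher grade is. An event that resolved and reappeared is not linked, so it remains a TEAE.
4. Define unique so that linked records count as one TEAE.

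Protocol 12.1.4.1 need not change. Restricting new records to worsening would alter data capture mid-study and lose the dated severity step-downs unless they were captured another way.

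The cost is a few sentences in the SAP, one programming rule, and a check of linkage in the data already entered. That check should be done before lock and while treatment assignments are still blinded. Since SAP 4.4.6.3 provides for Part 1 to be locked and unblinded for an interim analysis, the rule should be in place before that lock.

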12.2. Serious Adverse Events

12.2.1. Definition of a Serious Adverse Event

An SAE is any untoward medical occurrence, that at any dose:

- Results in death;
- Is life-threatening, ie, the subject is, in the opinion of the Investigator, at immediate risk of death from the event as it occurred, (it does not include an event that, had it occurred in a more severe form, might have caused death);
- Requires hospital admission or prolongs hospitalization. Planned hospital admissions or surgical procedures for an illness or a disease that existed before administration of study drug, and for which the condition has not worsened since starting study drug, are not to be considered SAEs. Emergency room visits that are less than 24 hours will also not be considered SAEs unless any of the other serious criteria is fulfilled;
- Results in persistent or significant disability or incapacity;
- Is a congenital anomaly/birth defect; or
- Is a medically significant event that, based on appropriate medical judgment, may jeopardize the subject and may require medical or surgical intervention to prevent one of the outcomes listed above.

Note: A distinction should be drawn between SAEs and severe AEs. Severity is a measure of the intensity of an AE, while the criteria for seriousness are indications of adverse subject outcomes for regulatory reporting purposes. A severe AE is not necessarily considered an SAE. For example, a headache that persists for several hours may be considered a severe AE but not an SAE. Conversely, a wound infection that may be considered minor could be an SAE if it prolonged hospitalization.

12.2.2. Reporting Serious Adverse Events

The Investigator and the Sponsor will monitor safety for this study. A Serious Adverse Event Report (SAER) Form is to be completed for each SAE occurring after signing of the ICF until 30 days after the last dose of study drug, regardless of causality.

All SAE reports must be **reported within 24 hours of the Investigator's knowledge of the event to [REDACTED]**. If requested by the Sponsor, any supporting documentation (eg, medical records) sent to [REDACTED] with the SAER Form must have subject identifying information (eg, subject names, subject addresses, medical records number) redacted by the site. Follow-up information to all SAEs should be submitted to the Sponsor, or designee, in the same timeframe as initial reports.

All SAEs will be followed until resolution or medical stabilization (in cases where resolution would not be expected).

In accordance with applicable regulations and local laws, the Sponsor or designee will report all serious and unexpected AEs assessed as related to study drug by the Investigator and/or Sponsor, to the regulatory authorities within the required timeframe. The Investigator will be responsible for reporting this safety information to his or her IRB/IEC.

If the Investigator becomes aware of an SAE any time after study completion and determines it is related to the study drug, the SAE must be reported to the Sponsor or designee within 24 hours of the Investigator's knowledge of the SAE.

12.2.3. Pregnancy

Pregnancy in and of itself is not an AE, although pregnancies occurring in subjects or partners of male subjects are considered immediately reportable events. If a pregnancy occurs in a subject, study drug must be discontinued immediately. The pregnancy must be reported to Innovaderm Drug Safety via email at [contact] within 24 hours of the Investigator's knowledge of the pregnancy using the Pregnancy Reporting Form.

The Investigator will follow the pregnant woman until completion of the pregnancy, and must notify the Sponsor, or designee, of the outcome within 24 hours of the Investigator's knowledge of the pregnancy outcome. The Investigator will provide this information on the Pregnancy Reporting Form. This notification includes pregnancies resulting in live, "normal" births.

If the pregnant subject experiences an SAE during pregnancy, or the outcome of the pregnancy meets the criteria for immediate classification as an SAE (ie, spontaneous abortion [any congenital anomaly detected in an aborted fetus is to be documented], stillbirth, neonatal death, or congenital anomaly), the Investigator should follow the procedures for reporting SAEs (ie, report the event to the Sponsor via email at [REDACTED] within 24 hours of the Investigator's knowledge of the event).

All neonatal deaths and congenital anomalies that occur within 30 days of birth (regardless of causality) should be reported as SAEs to the Sponsor or designee. In addition, any infant death or congenital anomaly occurring after study completion that the Investigator suspects is related to the in-utero exposure to the study drug should also be reported to the Sponsor or designee.

